8.4 Safety Analysis

The overall safety profile of study drug will be assessed in terms of the following safety and tolerability endpoints:

- Adverse events
- Clinical laboratory values (hematology, serum chemistry, coagulation studies, vitamin levels, lipid panel, and urinalysis)
- Standard 12-lead ECGs
- Vital signs
- Pulse oximetry

Safety endpoints will be analyzed based on the Safety Set (for each applicable treatment period). Only descriptive analysis of safety will be performed and no statistical testing will be performed.

8.4.1 Adverse Events

For analysis purpose, AEs will be categorized as pretreatment AEs, treatment-emergent adverse events (TEAEs), or post-treatment AEs:

Pretreatment AE: any AE that started before the first dose of study drug.

TEAE: any AE that increased in severity or that was newly developed at or after the first dose of study drug through the end of TE period.

Post-treatment AE: any AE that increased in severity or that was newly developed after the TE period.

For AEs with missing or partial start dates, AE start dates will be imputed according to the rules in [Appendix G \(Section 10.7\)](#).

An adverse event overview table will be provided with the following for TE period:

- Number of TEAEs (total number of TEAEs only)
- Subjects with any TEAEs
- Subjects with TEAEs by relationship
- Subjects with TEAEs by maximum severity
- Subjects with TEAEs leading to treatment discontinuation
- Subjects with TEAEs leading to treatment interruption
- Subjects with grade 3/4 TEAEs
- Subjects with related TEAEs
- Subjects with serious TEAEs
- Subjects with related serious TEAEs
- Subjects with TEAE leading to death

The following summary tables of TEAEs will be presented by treatment group:

- All TEAEs
- Grade 3/4 TEAEs
- TEAEs by strongest relationship
- TEAEs by maximum severity
- TEAEs leading to treatment discontinuation
- TEAEs leading to treatment interruption
- Related TEAEs
- Serious TEAEs
- Related serious TEAEs
- TEAEs leading to death

When summarizing the number and percentages of subjects, subjects with multiple occurrences of the same adverse event or a continuing adverse event will be counted once, and only the maximum severity level will be presented in the severity summaries, and the worst/highest relationship level in the relationship summaries.

The following summary tables will be presented by treatment showing number and percentage of subjects

- TEAEs and SAEs by SOC and PT
- TEAEs and SAEs by PT
- TEAEs and SAEs by SOC and PT and Severity

- TEAEs and SAEs by SOC and PT and Relationship

In addition, a listing containing individual subject adverse event data for TEAEs leading to treatment discontinuation, SAEs and all deaths will be provided separately, with a flag indicating the TEAE status for SAEs and deaths.

8.4.2 Clinical Laboratory

For the treatment emergent laboratory measurements, the raw values and change from baseline values of the continuous hematology and chemistry results will be summarized in SI units by treatment group at each scheduled time point. For hematology and chemistry, the number and percentage of subjects with abnormal low (<LLN) value and with abnormal high (>ULN) value at each scheduled time point will be summarized.

For LFT and CPK results (alanine aminotransferase [ALT], aspartate aminotransferase [AST], serum alkaline phosphatase [ALP], total bilirubin and CPK), the following additional analyses will be conducted:

- The number and percentage of subjects who meet the thresholds for LFT and CPK according to the criteria defined in [Appendix H \(Section 10.8\)](#) will be summarized by visit and during the TE period. The shift of the threshold criteria from baseline to post baseline will be summarized.
- For each LFT, the box plot of LFT value/ULN will be provided against visit.
- A scatter plot of maximum values of ALT versus maximum values of total bilirubin will also be presented. Note that the ALT and Total bilirubin values are presented on a logarithmic scale. The graph will be divided into 4 quadrants with a vertical line corresponding to 3xULN for ALT and a horizontal line corresponding to 2xULN for total bilirubin. A similar graph of maximum values of AST versus maximum values of total bilirubin will be presented as well.
- A listing of subjects with elevated LFT results during the TE period will be presented. For each subject in the listing, LFT assessments at all visits will be included.

Results of GI/Nutrition laboratory parameters (specified in SAP M2) will be summarized and subject data listings will be provided. The number and percentage of subjects with abnormal low (<LLN) value and with abnormal high (>ULN) value at each scheduled time point will be summarized for GI/nutritional parameter and listed separately. In addition, boxplots by visit will be provided for GI/Nutrition laboratory parameters.

Results of serum pregnancy test, urinalysis, and the urine/serum pregnancy test will be listed in individual subject data listings only.

In addition, a listing containing individual subject hematology, chemistry, and coagulation values outside the reference ranges will be provided. These listings will include data from scheduled and unscheduled time points.

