12.3.4.2 Clinical Laboratory Assessments

For the treatment-emergent laboratory measurements, the raw values and change from baseline values of the continuous laboratory parameters will be summarized in SI units by treatment group at each scheduled time point. In addition, mean value at each visit will be plotted by treatment groups for each of the liver function parameters.

The number and percentage of subjects with at least 1 potentially clinically significant (PCS) event during the TE period will be summarized by treatment group. The PCS (postbaseline) shift from baseline will also be summarized for selected laboratory parameters. The PCS criteria and the parameter selection criteria will be provided in the SAP.

Results of urinalysis and the serum pregnancy test will be listed in individual subject data listings only. In addition, a listing containing individual subject laboratory assessment values outside the reference ranges will be provided. This listing will include data from scheduled and unscheduled time points.

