6.2 Sample Size and Power

The primary endpoint is the absolute change from baseline of Total Brody/CF-CT score measured by the Brody/CF-CT score system at Week 72 using LDCT. The difference between the VX-661/ivacaftor group and the placebo group in the mean change from baseline in Total Brody/CF-CT score at Week 72 will be estimated.

This is an exploratory, Phase 2 study; the sample size is not based on statistical power. With 40 subjects (20 per arm), the study is aimed to explore changes in the Total Brody score over a 72 week period and for VX-661/ivacaftor versus placebo, based on the published literature^{1,2}.

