10.8 Appendix H: Threshold Analysis Criteria

Table 10-8 Threshold Criteria for Laboratory Tests

Parameter	Threshold Criteria	Comments
Clinical Chemistry		
CPK	>ULN - ≤ 2.5 x ULN >2.5 - ≤ 5 x ULN >5 - ≤ 10x ULN >10 x ULN	CTCAE grades 1-4
Creatinine	>ULN - ≤ 1.5 x ULN >1.5 - ≤ 3.0 x ULN >3.0 - ≤ 6.0 x ULN >6.0 x ULN	CTCAE grades 1-4
Blood Urea Nitrogen	>ULN - ≤ 1.5 x ULN >1.5 - ≤ 3.0 x ULN >3.0 - ≤ 6.0 x ULN >6.0 x ULN	Same criteria as creatinine No CTCAE
Sodium	Hyponatremia <LLN - ≥130 mmol/L <130 - ≥120 mmol/L <120 mmol/L Hypernatremia >ULN - ≤ 150 mmol/L >150 mmol/L - ≤155 mmol/L >155 mmol/L - ≤ 160 mmol/L >160 mmol/L	CTCAE grade 1, 3, 4 (No CTCAE grade 2) CTCAE grade 1-4
Potassium	Hypokalemia <LLN - ≥ 3.0 mmol/L <3.0 - ≥ 2.5 mmol/L <2.5 mmol/L Hyperkalemia >ULN - ≤ 5.5 mmol/L >5.5 - ≤ 6.0 mmol/L >6.0 - ≤ 7.0 mmol/L >7.0 mmol/L	CTCAE grade 1&2, 3, 4 (Grade 1 and 2 are the same) CTCAE grade 1-4
Total Cholesterol	>ULN - ≤ 7.75 mmol/L >7.75 - ≤ 10.34 mmol/L >10.34 - ≤ 12.92 mmol/L >12.92 mmol/L	CTCAE grade 1-4
Triglycerides	>1.71 - ≤ 3.42 mmol/L >3.42 - ≤ 5.7 mmol/L >5.7 - ≤ 11.4 mmol/L >11.4 mmol/L	CTCAE grade 1-4
Glucose	Hypoglycemia <LLN - ≥ 3.0 mmol/L <3.0 - ≥ 2.2 mmol/L <2.2 - ≥ 1.7 mmol/L <1.7 mmol/L Hyperglycemia >ULN - ≤ 8.9 mmol/L >8.9 - ≤ 13.9 mmol/L >13.9 - ≤ 27.8 mmol/L >27.8 mmol/L	CTCAE grade 1-4 CTCAE grade 1-4

Albumin	<LLN - ≥ 30 g/L <30 - ≥ 20 g/L <20 g/L	CTCAE grade 1-3
Amylase	>ULN - ≤ 1.5 x ULN >1.5 - ≤ 2.0 x ULN >2.0 - ≤ 5.0 x ULN >5.0 x ULN	CTCAE grade 1-4
Lipase	>ULN - ≤ 1.5 x ULN >1.5 - ≤ 2.0 x ULN >2.0 - ≤ 5.0 x ULN >5.0 x ULN	CTCAE grade 1-4
Direct bilirubin	>ULN - ≤ 1.5 x ULN >1.5 - ≤ 2 x ULN >2 - ≤ 3 x ULN >3 - ≤ 10 x ULN >10 x ULN	Same Criteria as Total Bilirubin No CTCAE Not in DILI Guidance
GGT	>ULN - ≤ 2.5 x ULN >2.5 - ≤ 5.0 x ULN >5.0 - ≤ 20.0 x ULN >20.0 x ULN	CTCAE grade 1-4
Calcium	Hypercalcemia >ULN - ≤ 2.9 mmol/L >2.9 - ≤ 3.1 mmol/L >3.1 - ≤ 3.4 mmol/L >3.4 mmol/L	CTCAE grade 1-4
	Hypocalcemia <LLN - ≥ 2.0 mmol/L <2.0 - ≥ 1.75 mmol/L <1.75 - ≥ 1.5 mmol/L <1.5 mmol/L	CTCAE grade 1-4
Magnesium	Hypermagnesemia >ULN - ≤ 1.23 mmol/L >1.23 - ≤ 3.30 mmol/L >3.30 mmol/L	CTCAE grade 1, 3, 4 No CTCAE grade 2
	Hypomagnesemia <LLN - ≥ 0.5 mmol/L <0.5 - ≥ 0.4 mmol/L <0.4 - ≥ 0.3 mmol/L <0.3 mmol/L	CTCAE grade 1-4
Bicarbonate	<LLN >ULN	No CTCAE
Inorganic phosphate	Hypophosphatemia <LLN - ≥ 0.8 mmol/L <0.8 - ≥ 0.6 mmol/L <0.6 - ≥ 0.3 mmol/L <0.3 mmol/L	CTCAE grade 1-4

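### SAP 8.4.2 applies its laboratory threshold criteria to 5 of 26 analytes and states no selection rule, so the rest have no graded by-arm count over the treatment-emergent period

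*SAP*

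**What the plan says.** Protocol 12.3.4.2 makes three statements in sequence:

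- The count: "The number and percentage of subjects with at least 1 potentially clinically significant (PCS) event during the TE period will be summarized by treatment group". This sentence does not limit the analytes.
- The shift: "The PCS (postbaseline) shift from baseline will also be summarized for selected laboratory parameters". The restriction to selected parameters is attached here.
- The delegation: "The PCS criteria and the parameter selection criteria will be provided in the SAP".

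SAP Appendix H then supplies "Table 10-8 Threshold Criteria for Laboratory Tests", with graded categories for most chemistry and hematology analytes, and a separate Table 10-9 for coagulation.

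SAP 8.4.2 calls on Appendix H once: "The number and percentage of subjects who meet the thresholds for LFT and CPK according to the criteria defined in" that appendix, by visit and over the TE period. It lists the tests meant as ALT, AST, ALP, total bilirubin and CPK. Other hematology and chemistry results get by-visit descriptive summaries and counts below LLN or "with abnormal high (>ULN) value at each scheduled time point will be summarized". Hematology, chemistry and coagulation values outside the reference range are also listed, with unscheduled draws included.

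**The concern.** The protocol plans a by-arm count of subjects with at least one PCS value during the TE period. The SAP writes criteria that could deliver it for 26 analytes, uses them for five, and does not say how the five were chosen. Renal function, electrolytes, glucose, pancreatic enzymes and all of hematology have thresholds that lead to no stated table.

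Safety is the secondary objective visible in both documents. For the unused analytes, the planned counts do not separate a marked abnormality from a value just outside the range. They also do not accumulate over the TE period, and they can drop an unscheduled value when another record in the same window lies closer to the target day.

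**Working it through.** **1. Count of analytes.** Inputs: the rows of SAP Table 10-8 and the list in SAP 8.4.2. Four further rows of Table 10-8 combine ALT, AST and total bilirubin and are not counted as separate analytes. The documents state no figure of their own to reproduce.

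| Group | Criteria in Table 10-8 | Named in 8.4.2 | Not named |
|---|---|---|---|
| Chemistry | 21 | 5 | 16 |
| Hematology | 5 | 0 | 5 |
| Total | 26 | 5 | 21 |

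21/26 = 81%. The 16 chemistry analytes are creatinine, urea nitrogen, sodium, potassium, total cholesterol, triglycerides, glucose, albumin, amylase, lipase, direct bilirubin, GGT, calcium, magnesium, bicarbonate and inorganic phosphate. The five hematology analytes are WBC, lymphocytes, neutrophils, hemoglobin and platelets.

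**2. How firm is 21?**

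- Protocol 11.6.3 counts GGT and direct bilirubin as liver function tests. Reading them into the SAP's term gives 26 − 7 = 19 (73%).
- The bicarbonate criteria are simply below LLN and above ULN, which the by-visit counts already cover. Only its TE-period count is missing, so 20 analytes lack the threshold count altogether.
- Adding aPTT, PT and INR from Table 10-9 gives 26 + 3 = 29 parameters, of which 29 − 5 = 24 are unused.

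**3. Comparison within the SAP.** SAP 8.4.3 and 8.4.4 each contain a general sentence applying the Appendix H criteria by treatment during the TE period. SAP 8.4.2 has no such sentence. Table 10-11 also refers to the ECG heart-rate criteria as PCS, which ties Appendix H to the protocol's term.

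**4. What the by-visit counts do with unscheduled values.** Under SAP 8.1, when a window holds several safety records, the one closest to the target day is used.

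- *Hematology.* Table 10-3 gives Week 24 a window of days 2 to 253, that is 253 − 2 + 1 = 252 days, with target day 169. An unscheduled platelet count on day 40 is 169 − 40 = 129 days from target. The scheduled draw, allowed ± 1 week, is at most 7 days away. The day-40 value is displaced from every by-visit table.
- *Chemistry.* At Weeks 24, 36, 48 and 60 only liver tests are drawn from the chemistry panel. Of the 16 unused chemistry analytes, two (GGT, direct bilirubin) are in the protocol's liver set. Two more (total cholesterol, triglycerides) are in the lipid panel drawn at Weeks 24 and 48. The remaining 16 − 2 − 2 = 12 have no scheduled draw between Week 12 (target day 85) and Week 72 (target day 505), a gap of 505 − 85 = 420 days, unless the subject stops early. An unscheduled value in most of that gap maps to a Week 24 to Week 60 window. The SAP does not say whether a row is printed for a visit at which the analyte is not scheduled.

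**5. Grading.** Table 10-8 splits low potassium into LLN to 3.0, below 3.0 to 2.5, and below 2.5 mmol/L. A value of 2.4 falls in the lowest category. In the by-visit count it is one subject below LLN, the same as a value just under LLN.

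**6. Use of extremes.** SAP 8.1 includes unscheduled values when deriving on-treatment maxima and minima, but no table stated in 8.4.2 uses those extremes for the 21 analytes.

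**The case against.** The strongest reply is that the protocol hands parameter selection to the SAP and the SAP names its parameters. A liver focus also fits a trial in which only liver tests are drawn from the chemistry panel between Weeks 24 and 60. A reader might infer a plain breach of the protocol. The documents do not support that, because the delegation is explicit. What stands against the SAP is narrower: the protocol asked for selection criteria, and none is given.

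A reader might also infer that a marked abnormality in the 21 analytes reaches no by-arm table. That is too strong, for three reasons:

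- Protocol 11.6.2 and 13.1.1.2 make clinically significant laboratory results adverse events. SAP 8.4.1 tabulates TEAEs by treatment group, including by maximum severity and Grade 3/4, whether or not the draw was scheduled. This route depends on the investigator's judgement, and Protocol 13.1.1.2 prefers a diagnosis to the test result, so it does not reproduce a threshold count.
- By-visit summaries for chemistry and hematology show minimum and maximum, so a windowed potassium of 2.4 mmol/L would be visible. For coagulation that summary rests on Protocol 12.3.4.2, because the SAP sentence names only hematology and chemistry.
- With about 20 subjects per arm, the out-of-range listing is readable.

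Finally, GI/nutrition parameters are assigned to a document called SAP M2, and IDMC analyses to a separate IDMC SAP. Neither is available here, so it cannot be said that the criteria are used nowhere. Appendix H may also be carried over in part from other studies: Table 10-11 has weight criteria, yet 8.4.4 does not analyse weight. That would explain the mismatch but does not resolve it.

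**Conclusion.** The point holds as a gap in the planned safety tables. Of 26 analytes with criteria in Table 10-8, 21 feed no threshold analysis stated in this SAP. The figure is 19 if GGT and direct bilirubin are read in as liver tests, and for bicarbonate only the TE-period count is missing. The coagulation criteria in Table 10-9 are also unused. No parameter selection rule is given.

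The missing item is a graded by-arm TE-period count that includes unscheduled values and does not depend on whether an investigator called the value clinically significant. The other outputs reduce the consequence but do not replace that count.

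Severity is low to moderate. Safety is analysed descriptively, and no primary estimate, interval or conclusion changes. The verdict assumes that the SAP's bracketed list is meant as complete, and it covers only the SAP text available here.

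**What to change.** Add one table to SAP 8.4.2: for every parameter in Tables 10-8 and 10-9, show by treatment group the count and percentage of Safety Set subjects in each worst threshold category reached during the TE period, using scheduled and unscheduled values. Where a parameter has both low and high criteria, tabulate the two directions separately. The protocol's at-least-one-event count can then be read by adding categories from whichever cut is called PCS.

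Keep the existing by-visit counts below LLN and above ULN and the LFT/CPK by-visit threshold tables. Write by treatment group into the LFT/CPK threshold sentence, which does not say so itself. Limit baseline-to-worst shifts to selected parameters, as the protocol does, and name them.

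If the sponsor prefers to stay with five analytes, the minimum is to state and justify the selection rule and remove the unused criteria. That settles the mismatch but leaves the graded count missing.

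The cost is a short SAP change before database lock, reuse of the LFT/CPK table program, and a few more pages of safety tables. No new data are needed.

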8.4.3 Standard 12-Lead Electrocardiogram

For the treatment emergent ECG measurements, a summary of raw values and change from baseline values will be provided by treatment group at each scheduled time point for the following standard 12-lead ECG measurements: PR, QT, and QTc for HR intervals (QTcF), QRS duration, and HR.

The number and percentage of subjects with ECG event meeting threshold criteria during the treatment-emergent period will be summarized by treatment, ECG parameters, and visit. The threshold criteria are provided in [Appendix H \(Section 10.8\)](#).

8.4.4 Vital Signs

For the treatment emergent vital signs measurements, the raw values and change from baseline values will be summarized by treatment group at each scheduled time point: systolic and diastolic blood pressure (mm Hg), body temperature (°C), HR (beats per minute), and respiratory rate (breaths per minute).

The number and percentage of subjects with vital signs meeting threshold during the treatment-emergent period will be summarized by treatment, vital signs parameters, and visit. The threshold criteria are provided in [Appendix H \(Section 10.8\)](#).

8.4.5 Pulse Oximetry

For the treatment emergent pulse oximetry measurements, a summary of raw values and change from baseline values will be provided by treatment groups at each scheduled time point for the percent of oxygen saturation by pulse oximetry.

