12.3.4.6 Other Safety Analysis

12.3.4.6.1 Pulse Oximetry

For the treatment-emergent pulse oximetry measurements, a summary of raw values and change from baseline values will be provided by treatment groups at each scheduled time point for the percent of oxygen saturation by pulse oximetry. In addition, the mean value at each visit will be plotted by treatment group for the percent of oxygen saturation.

The number and percentage of subjects with shift changes from baseline (normal/missing and low according to the reference range) to the lowest percent of oxygen saturation during the TE period will be tabulated by treatment group.

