8 STATISTICAL ANALYSIS

8.1 General Considerations

The Schedule of Assessments is provided in [Appendix A \(Section 10.1\)](#).

All individual subject data for those randomized or exposed to study drug will be presented in data listings.

Continuous variables will be summarized using the following descriptive summary statistics: the number of subjects (n), mean, standard deviation (SD), standard error (SE), median, minimum value (min), and maximum value (max).

Categorical variables will be summarized using counts and percentages.

Baseline Value, unless otherwise specified, is defined as the most recent non-missing measurement (scheduled or unscheduled) collected prior to the first dose of study drug. For ECGs, the baseline will be defined as the average of the 3 pretreatment measurements (triplicate) on Day 1.

Absolute Change from baseline will be calculated as Postbaseline value - Baseline value.

Relative change from baseline will be calculated and expressed in percentage as $100\% \times (\text{Postbaseline value} - \text{Baseline value}) / \text{Baseline value}$.

Treatment Emergent (TE) Period will include the time from the first dose to Safety Follow-up Visit. For subjects who do not have a Safety Follow-up Visit because they rolled over into the open-label extension study within 28 days after the last dose of study drug, the end of the TE period will be the date of rollover into the extension study. For subjects who do not have a Safety Follow-up Visit and did not roll over into the extension study, the end of the TE period will be 28 days after the date of last dose. The TE period will be used for safety analyses unless otherwise specified.

Unscheduled Visits: Unscheduled visit measurements will be included in the analysis as follows:

- In scheduled visit windows per specified visit windowing rules;
- In the derivation of baseline and last on-treatment measurements;
- In the derivation of maximum/minimum on-treatment values and maximum/minimum changes from baseline values for safety analyses;
- In individual subject data listings where appropriate.

Visit Windowing Rules: The analysis visit windows for protocol-defined visits are provided in [Appendix B \(Section 10.2\)](#). The windows will be applied using the following rules for both scheduled and unscheduled visits:

1. If no measurement is available within a visit window, the assessment will be considered missing for the visit;

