2. If there is more than one measurement available within the same visit window, use the following rules:

For all efficacy parameters, if there are multiple measurements within a visit window, the record at the scheduled visit will be used. Otherwise,

- If there are no measurements at the scheduled visit, then the record closest to the target day will be used;

- If there are multiple records with the same distance to the target day, the latest record will be used.
- Assessments at early treatment termination (ETT) visit will follow the windowing rules for regular visits up to Week 72.
- Assessments at safety follow-up (SFU) visit will follow the windowing rules for regular visits if it falls within the upper boundary of the window for Week 72, or remain as SFU if it goes beyond the upper boundary of the window for Week 72.

For all safety parameters, if there are multiple measurements within a visit window, then 1) the record closest to the target day will be used; 2) if there are multiple records within the same distance from the target day, the latest record will be used; or 3) SFU visit will not be windowed, instead, used per nominal visit in relevant analyses.

Incomplete/Missing data will not be imputed, unless otherwise specified.

Outliers: No formal statistical analyses will be performed to detect or remedy the presence of statistical outliers, unless otherwise specified.

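### SAP 8.4.5 omits the protocol's by-arm shift table to lowest oxygen saturation and its mean plot; SAP 8.4.2 also leaves coagulation without a by-arm summary

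*SAP*

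**What the plan says.** Pulse oximetry and coagulation studies are both part of the secondary safety endpoint (Protocol 7.2; SAP 5.2).

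**Pulse oximetry.** Protocol 12.3.4.6.1 plans three outputs:
- by-visit summaries of raw values and change from baseline, by arm;
- a plot: "the mean value at each visit will be plotted by treatment group for the percent of oxygen saturation";
- the number and percentage of subjects shifting from baseline category (normal/missing, or low) "to the lowest percent of oxygen saturation during the TE period will be tabulated by treatment group".

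SAP 8.4.5 is a single sentence: "For the treatment emergent pulse oximetry measurements, a summary of raw values and change from baseline values will be provided by treatment groups". Its remaining words only say that this is done per scheduled visit for percent saturation.

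**Coagulation.** Protocol 12.3.4 lists coagulation studies among the clinical laboratory values. Protocol 12.3.4.2 then says that "the raw values and change from baseline values of the continuous laboratory parameters will be summarized in SI units by treatment group" and makes only urinalysis and the serum pregnancy test listing-only. SAP 8.4.2 is narrower: "the raw values and change from baseline values of the continuous hematology and chemistry results will be summarized in SI units by treatment group". It treats GI/nutrition parameters separately and mentions coagulation only in a listing of values outside the reference range.

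**The concern.** Desaturation matters as a low value in an individual. The protocol's shift table is the output built for that: it takes each subject's lowest value over the whole treatment-emergent period and counts subjects by arm. A by-visit summary describes a distribution at one time point and does not say how many subjects in each arm were ever low. If the SAP is followed as written, the report will lack a protocol-specified comparison for a named safety endpoint, with no reason given in the visible text. It will also have no by-arm summary of coagulation values.

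**Working it through.** There is no design figure to reproduce. The protocol states that the sample size of about 40 (20 per arm) is not based on power. The check sets the two documents side by side.

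**1. Pulse oximetry outputs.**
- By-visit raw and change summaries: protocol yes, SAP 8.4.5 yes.
- Plot of means by visit: protocol yes, SAP no.
- Shift to lowest saturation, by arm: protocol yes, SAP no.

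The SAP keeps 1 of 3.

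**2. Whether another SAP section replaces the shift table.** SAP 8.4.4 counts subjects meeting vital-sign thresholds, but Table 10-11 covers heart rate, systolic and diastolic pressure, and weight. Table 10-10 covers ECG parameters, and Tables 10-8 and 10-9 cover laboratory tests. None has a saturation criterion. The adverse event tables in SAP 8.4.1 count a desaturation only if it was reported as an event.

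**3. What the by-visit summary can show.** SAP 8.1 defines a continuous summary as n, mean, SD, SE, median, minimum and maximum. As an illustration, assume 20 subjects in an arm, one of whom falls from 97% to 87% at one scheduled visit, and a reference range that classes 87% as low. The documents give neither these saturation values nor the range.
- Shift in the arm mean at that visit: (97 − 87)/20 = 0.5 points.
- The 87% is visible if it is that arm's minimum at that visit.
- Shift table: 1/20 = 5%.

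The minimum shows that at least one subject was low at that visit. It does not give the number who were low at any time.

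**4. Which readings enter the summary.** When a window holds several safety records, SAP 8.1 says "the record closest to the target day will be used". The Week 24 window in Table 10-3 is Days 128 to 211, which is 211 − 128 + 1 = 84 days around target Day 169. A visit held within ±7 days falls within a span of 15 days. If that visit's reading exists, a reading on any of the other 84 − 15 = 69 days is further from target and is not used. This shows how the rule works. It is not an estimate of how many readings are lost, because the documents do not say how often unscheduled oximetry is taken.

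**5. What the SAP already allows.** SAP 8.1 includes unscheduled measurements when minimum on-treatment values are derived for safety analyses. Section 8.4.5 never calls for such a minimum for saturation.

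**6. Coagulation.** Protocol 12.3.4 and 12.3.4.2 together bring coagulation into the by-arm raw and change summaries. SAP 8.4.2 limits those summaries, and the below- and above-range counts, to hematology and chemistry, with GI/nutrition parameters handled separately. It calls for threshold counts only for liver function tests and CPK. Yet Table 10-3 gives coagulation a Week 72 window (Days 464 to 519), and Table 10-9 grades PTT and PT/INR. No analysis text uses either for coagulation.

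**The case against.** Several stronger readings are tempting, and the documents do not support them.

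- **A reader might infer that the SAP reports means only.** It does not. Minimum and maximum are part of every continuous summary, and individual data are listed for about 40 subjects. A low reading at a scheduled visit can be seen.
- **A reader might infer that low unscheduled readings are usually lost.** No figure supports that. The footnote on vital signs and oximetry in Protocol Table 3-2 provides for extra symptom-targeted vital signs and does not name oximetry. An unscheduled reading does enter the summary when it is the closest record in its window.
- **A reader might infer that no by-arm count of desaturation or coagulation abnormality can exist.** Clinically significant laboratory abnormalities are reported as adverse events (Protocol 11.6.2). Clinically significant worsening on study assessments is also documented as an event (13.1.1.2, whose list is open but does not name oximetry). Treatment-emergent events are counted by arm. That route depends on investigator judgment and does not count category shifts as such.
- **A reader might infer that the protocol demands counts by Table 10-9 category.** It does not. It leaves the criteria and parameter selection for potentially clinically significant values to the SAP. Unused thresholds are not peculiar to coagulation either: Table 10-8 grades creatinine, sodium and hemoglobin, among others, without a count being called for in 8.4.2.

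It is also fair to say that the study is exploratory, that safety analysis is descriptive, and that the IDMC reviews safety under its own charter and SAP. Protocol 12.3 leaves details to the SAP, and 12.3.4.2 reaches coagulation through a general phrase rather than by name. These points limit the importance of the omissions, and the coagulation point is the weaker of the two. They do not explain why a table that the protocol describes explicitly is absent.

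**Conclusion.** The point holds as a mismatch between protocol and SAP. Two of the three pulse oximetry outputs in the protocol are missing. The one that matters is the lowest-saturation shift table, because apart from adverse event reports nothing else planned counts subjects with low saturation by arm. A lower unscheduled value that is not closest to the target day goes unsummarized, though listed; how often that would happen cannot be stated from the documents. The coagulation gap is real but smaller. It rests on reading Protocol 12.3.4.2 together with 12.3.4, and after baseline coagulation is scheduled only at Week 72 and Safety Follow-up. Both omissions affect reporting of secondary safety endpoints. Neither touches the primary endpoint, its analysis or data collection. They should be corrected because the protocol specifies the outputs and the correction is cheap.

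**What to change.** - **SAP 8.4.5:** restore the by-arm table of baseline category (normal/missing, low) against lowest saturation in the treatment-emergent period. Derive the lowest value under the existing SAP 8.1 rule that minimum on-treatment values include unscheduled measurements. Restore the by-visit plot of mean saturation.
- **SAP 8.4.2:** add coagulation to the by-arm summary of raw values and change from baseline, using the windows already in Table 10-3. Counts by Table 10-9 category would be an optional addition.
- If either omission was deliberate, state the departure from the protocol and the reason in the SAP.

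The cost is SAP wording, a few tables and one plot, all from data already collected.
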